4.2 Intervention structure

This will be a 10 session, 12-week in-person, video, and/or phone-based support program with assessment for 2 weeks before and 1 week after treatment visits. The treatment will center on providing CVD health education, with a focus on behaviors to address modifiable risk, goal-setting support, and resource and care coordination. Modality of treatment delivery (in-person, phone, or video platform) will be adapted based on logistics by study team considering participant preference as well as safety in case of changes in the status of COVID-19 in our community.

In-person assessment and treatment visits will be conducted in private spaces at Catholic Charities' facilities, at sites convenient to participants, or at HHRI/HHS. All in-person assessment and treatment visits will follow current guidance from HHRI and Hennepin Healthcare about social distancing and use of personal protective equipment. Video visits will be conducted via a secure Zoom or Teams link (using HHRI or Hennepin Healthcare HIPPA secure technology). Phone visits will be conducted via a study cellphone or office phone or using the secure TelemedIQ app of study team members.

Psychological approaches of behavioral activation and motivational interviewing will be used along with provision of educational materials and tools to support behavior change. Which educational materials are given to which participants will be decided by the coach depending on participant need, learning preferences, and the specific goals that are mutually set.

Participants will each receive a tool of approximately \$20 commercial value. Tools will be chosen by coaches and participants collaboratively to reinforce health behavior change goals. E.g. A participant with 10 medications per day may benefit from a pillbox with AM and PM slots, and a participant with many appointments for behavioral and physical health care may benefit from a pocket calendar. Some participants who choose to work on quitting smoking may select tools of nicotine lozenges or patches (see safety protocol, pregnancy in inclusion/ exclusion criteria). These tool choices are based on extensive qualitative development work with patients and providers (R03HL136540, Aim 1 interviews of this project).

To facilitate follow-up with this population, we will ask participants to provide multiple modalities by which we may contact them, including phone, email, and secondary contacts.

While study visits may occur by phone, email communications will be limited to content only related to arranging details of when/where and how to connect with participants or sharing resources or educational materials with permission. Participants will provide their email addresses and provide signed consent to be contacted in this way. Privacy concerns and appropriate use of email to arrange for other communication with study team will be noted in the consent.

We will also ask participants to identify two people who know them well and would know how to reach them if we are not able to contact them by phone or email. Similarly, we will ask participants to identify medical and social service providers who would know their current contact information for them. Participants will be asked to sign appropriate releases of information to allow medical and social service providers to share this information with the study team.

4.2.1 Wellness coaching content

Session 1 will acclimate the patient to the coaching program and inform future goal setting. Coaches will collaboratively identify an initial health behavior target (i.e., eating better, being more active, taking medications as prescribed, quitting tobacco, or getting healthy sleep; the patient must be currently below recommended guidelines and willing to work on improvement), and provide self-monitoring activities to track mood and health behaviors. **Session 2** will include review of patient self-monitoring of mood, activities, and target health behavior, emphasizing mood/behavior relationships, a structured values assessment to identify life areas that the participant cares deeply about; this was adapted by our Quorum team for people experiencing homelessness. Values will be used to set 2-4 goals that can be completed before the next session. Starting at session 2, participants will work with coaches to identify an affordable, commercially available behavior change tools related to their relevant health behavior and tailored to patient preferences and comorbidities as above. **Session 3-10** will follow the same format to assess wellness (mood), activity, and relevant health behavior between sessions, review adherence to goals from the previous session, address barriers, and choose 2-4 new between session goals. Starting in session 4 the collaboratively discussions will consider adding 1-2 relevant health behaviors.

In addition to the coaching tools submitted in the IRB, coaches will provide audio, video, or written materials based on participant interest and preferred learning style. These materials will be selected from the American Heart Association (<https://www.heart.org/en/healthy-living/healthy-lifestyle/lifes-essential-8>) and American Diabetes Association (<https://diabetes.org/>) directly or other respected partners who create easy-to-read handouts aligned with recommended guidelines (e.g., <https://learningaboutdiabetes.org/> or <https://www.diabeteseducator.org/living-with-diabetes/Tools-and-Resources>).

4.2.2 Final Assessment

The final assessment visit will be completed within 4 weeks of completion of visit 10 or upon early termination. This will be completed by a research staff member who is distinct from the interventionist. See list of measures in Table 2 and Assessment Table.

4.3 Unscheduled Visits

Contact between the study team and participant during the 16 week intervention period will be encouraged. This will include reminders of study-related assessments and visits. The interventionist will work with the patient to set treatment goals related to improved CV health. These may include between-visit text messages, calls, e-mails, or private messages on secure social media platforms per the participant's preference. These will be done with input and agreement by the participant. The interventionist will also respond to participant-initiated between visit communications. Should communications become too frequent or surpass agreed upon treatment boundaries, the interventionist will be guided to set boundaries and limit contact with guidance from [name].

4.4 Concomitant Treatment

All prior and concomitant primary care and cardiovascular care will be reviewed as needed to support study goals. Care for relevant co-morbidities (mental illness, substance use disorder, cardiac disease, etc.) will also be noted and encouraged as it aligns with participant psychological wellness or CV health (e.g., follow-up with psychiatry or cardiology).

4.5 Rescue Medication Administration *Not applicable in this behavioral trial.***4.6 Participant Completion/Withdrawal**

Participants may withdraw from the study at any time without prejudice to their care. They may also be discontinued from the study at the discretion of the Investigator for lack of adherence to study treatment or visit schedules and adverse events (AEs). If the Investigator becomes aware of any serious, related adverse events after the participant completes or withdraws from the study, they will be recorded in the source documents and on the case report form.

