Statistical And Analytic Plan	
The primary endpoint of this study is the feasibility and acceptability of the program to participants in this treatment development phase. We will summarize themes in the end-of treatment interview, assess satisfaction via structured survey, and assess treatment dose received via frequency, length, and type of communications with study staff.
 
We will conduct exploratory analyses on our eventual primary behavioral endpoint of cardiovascular health. We will refine our use of patient-reported outcomes for use in a future randomized pilot trial.

Data And Safety Monitoring Plan	
[name] (PI) will work closely with study staff to monitor the quality of data collected at assessment. This treatment development study (N=8), does not meet NIH criteria requiring a Data Safety Monitoring Board (DSMB), however [name] will oversee a detailed safety monitoring plan.

TABLE 1: SCHEDULE OF STUDY PROCEDURES

Study Phase	Eligibility screening	Consent, Baseline assessment	Treatment sessions										Follow-up visit
			1	2	3	4	5	6	7	8	9	10	
Visit Number			1	2	3	4	5	6	7	8	9	10	
Study Weeks	0	1	2-3	4	5	6	7	8	9	10	11	12	13-16
Confirm communication preferences	X	X	X				X						X
Review Inclusion/Exclusion Criteria	X	X											
Informed Consent		X											
Demographics/Medical History, experiences of discrimination		X											
Vital Signs: BP, HR		X											X
Height and Weight		X											X
Point of care LDL and blood glucose		X											X
Skin Carotenoids		X											X
Medication review		X											X
Self-report survey measures		X											X
Satisfaction with intervention													X

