Primary outcomes of this proof-of-concept, single arm, treatment development pilot trial are feasibility (e.g., recruitment, treatment engagement, retention) and acceptability (of study procedures and CV-HOMES treatment via satisfaction survey and post-treatment interview). Secondary outcomes will include efficacy measures we plan to use in a future randomized pilot study and eventual R01 randomized trial. Outcomes will be collected during screening and at a baseline and post-treatment assessment visits. We will examine feasibility by tracking success of planned methods of recruitment. We will track the ratio of invitations to screenings and screenings to enrollments. We will also examine treatment engagement and retention via the number of attended assessment visits and coaching sessions. We will use the 8-item Client Satisfaction Questionnaire and a 20 minute qualitative post-treatment exit interview to track acceptability of activities as has worked well in several prior trials by our team.¹⁷

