3.1.3 Follow-up

Participants who have completed their planned coaching sessions or requested to end their coaching sessions early will be contacted for a follow-up assessment. Participants will be informed of results in lab letter after appointment (2023.12.21 CV-Homes.LabLetter). Since the emphasis of this treatment development study is feasibility and acceptability, those ending early will be given particular attention during their post-treatment interview so that their insights and experiences can shape future adaptations to the intervention and study design.

3.2 Allocation to Groups and Blinding *Not applicable to this phase of the study.*

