4.6.1 Early Termination Study Visit

Any participant who withdraws will be contacted by [name] to assess their desired level of participation. A final assessment visit with compensation will be offered to those who are willing to ensure we collect data about why the intervention or protocol did not meet their needs. Participants will have the right to decline this visit if they desire.

5 STUDY EVALUATIONS AND MEASUREMENTS**5.1 Screening and Monitoring Evaluations and Measurements**

Our pre-consent phone screening (included in data collection materials) will closely parallel the phone screening used by [name] in a prior, similar study (HSR#17-4351). This was efficient and well-tolerated by participants in that study. The primary goal will be to ensure eligibility and interest in study participation.

During the baseline and final assessment visits, study staff will read questionnaire items out loud to participants and record information directly into REDCap. See our Assessment Table for a list of all measures.

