6 STATISTICAL CONSIDERATIONS

6.1 Primary Endpoint

Primary outcomes The primary endpoint of this study is the feasibility and acceptability of the program to participants in this treatment development phase. We will assess this by measuring our ability to recruit and retain participants, the dose of treatment we can deliver (i.e., participant's attendance and follow-up with scheduled sessions and treatment activities), and participants' report of their satisfaction and overall experience during participation in a structured survey (CSQ-8) and qualitative post-treatment interview. Secondary outcomes will include measures we plan to use in a future randomized pilot study (see Assessment Table).

Clinical Outcomes will occur at baseline and post-treatment. Our primary target is a composite measure of cardiovascular health developed by the American Heart Association, Life's Essential 8 (see Table 2).¹⁸ All biometric data and self-reported items will be collected and stored in REDCap.

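### Could participants whom the investigator discontinues for poor adherence miss the satisfaction survey and exit interview?

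*Combined protocol and SAP*

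**What the plan says.** **Ending participation.** Section 4.6 of the protocol first lets participants withdraw at any time. It then gives a second route out, in these words: "discontinued from the study at the discretion of the Investigator for lack of adherence to study treatment or visit schedules and adverse events (AEs").

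**Primary endpoint.** For feasibility and acceptability, section 6.1 states: "We will assess this by measuring our ability to recruit and retain participants, the dose of treatment we can deliver". It adds satisfaction on the CSQ-8 and a qualitative interview after treatment. Section 1.3 tracks "treatment engagement and retention via the number of attended assessment visits and coaching sessions", without naming a denominator.

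**Timing.** In Table 1 the row "Satisfaction with intervention" is marked only at the follow-up visit.

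**Who gets the final visit.** Three passages bear on this:

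- Section 3.1.3: "Participants who have completed their planned coaching sessions or requested to end their coaching sessions early will be contacted for a follow-up assessment". It adds that "those ending early will be given particular attention during their post-treatment interview so that their insights and experiences can shape future adaptations".
- Section 4.6.1: "Any participant who withdraws will be contacted by" a named team member. A paid final visit is then offered to the willing, who remain free to refuse.
- Section 4.2.2: the final assessment takes place "within 4 weeks of completion of visit 10 or upon early termination".

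**The concern.** The ground for discontinuation, poor adherence to coaching or visits, is itself part of what the study measures. Section 4.6 speaks of leaving the study, not only the coaching. Sections 3.1.3 and 4.6.1 mention completers, people who ask to stop and people who withdraw, but not those whom the investigator ends.

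If staff followed only those two sections to the letter, the two direct measures of acceptability would be missing for people selected on low engagement. The CSQ-8 summary could then look too favourable. The study would also lose interviews that 3.1.3 says it particularly wants. Section 6.2 does not say how missing CSQ-8 or interview data are handled, and retention could be reported over more than one denominator.

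**Working it through.** **Inputs.** The planned sample is 8 (section 3.3.2, which allows enrolment to stop sooner). Section 6.3 justifies that number in words only, so there is no calculation to reproduce. The documents give no rate of investigator discontinuation, no acceptance rate for a final visit and no expected CSQ-8 difference.

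**Step 1: does the text exclude these participants?**

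| Section | What it covers | Bearing on investigator-ended participants |
|---|---|---|
| 3.1.3, first sentence | Completers and those asking to stop | Silent |
| 3.1.3, last sentence | Early enders in general | Includes them on its wording |
| 4.2.2 | Timing of the final assessment, including early termination | Includes them; no limit on who decides |
| 4.6, last sentence | Serious related events learned of later | Recognises only completing and withdrawing |
| 4.6.1 | Those who withdraw; headed Early Termination Study Visit and placed under 4.6 | Depends on the meaning of withdraw |
| 8.4 and 9.4.1 | Independent professionals may recommend withdrawal | Withdrawal can be a study-side decision |

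The last sentence of 4.6 is informative. It comes directly after the discontinuation rule and knows only two ways out. If withdrawing meant the participant's choice alone, serious related events in discontinued people would fall outside the recording rule, which cannot be intended. With the usage in 8.4 and 9.4.1, the natural reading of 4.6.1 is that it covers every early ending. That agrees with 4.2.2.

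**Step 2: scale, if the narrow reading were followed.** Let *m* be the number ended by the investigator with no final visit, and *d* the points by which their CSQ-8 would have fallen below the others' mean. Both are assumptions.

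- Share unobserved = *m*/8: 1/8 = 12.5%, 2/8 = 25%.
- Excess in the reported mean = *m* × *d*/8: 0.125*d* for *m* = 1, 0.25*d* for *m* = 2.
- Chance of at least one such person at an assumed rate *p* each, with independence = 1 − (1 − *p*)^8: 34% at *p* = 5%, 57% at 10%, 83% at 20%, 94% at 30%.

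The range from 34% to 94% reflects only the choice of *p*. It also assumes that no visit is offered to anyone ended this way.

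**Step 3: retention.** With everyone else attending, retention over all enrolled is 7/8 = 87.5% for *m* = 1 and 6/8 = 75% for *m* = 2. A figure of 7/7 or 6/6 = 100% appears only if discontinued people are dropped from the denominator. No passage proposes that. Section 1.3 works with counts of attended visits and sessions, and section 5.4 already monitors how often people end early.

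**Step 4: what does not depend on a final visit.** Section 6.2.2 summarises contacts by type and initiator, minutes of treatment and session notes. These exist for everyone coached, including anyone later discontinued.

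**The case for a change.** The strongest case for a change has four parts.

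- Section 4.6 sets out withdrawal and discontinuation as separate routes, so a careful reader may take 4.6.1 as covering only the first. Its opening step, asking about the person's desired level of participation, suits someone who chose to leave.
- Section 4.2.2 says when the visit happens and who conducts it, not who is invited.
- Any resulting gap would be selected on the outcome. It would also touch the stated objective of measuring cardiovascular risk at two time points.
- A clarifying sentence would cost almost nothing.

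The first two points show that the wording is not uniform, and that stands. They do not show an exclusion, because the narrow reading conflicts with the rest of 4.6 and with 8.4 and 9.4.1. The third point is right about direction. Yet harm needs four things together: the discretion is used, no visit is offered, the person would have come, and the rating would have been lower. People ended for missing visits are also among the less likely to attend another. The 4-week catch-up window (3.3.1), the backup contacts (4.2) and the reminders (4.3) already work against loss through missed visits.

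The fourth point is fair, but a low price does not make an edit necessary. The Assessment Table cited in 4.2.2 is not in the available text, so the timing argument rests on Table 1 and section 1.3.

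**Conclusion.** No change follows. Read as a whole, the protocol already provides the CSQ-8 and exit interview for early enders who are willing, whoever ended their coaching. The contact sentences are looser than 4.2.2, and the retention denominator and the reporting of missing questionnaires are unstated. An analyst would fill these gaps sensibly: the analyses are descriptive, no test, threshold or progression rule depends on the CSQ-8, and with 8 participants each absent questionnaire is plain to see.

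The only firm figure is that one person is 12.5% of the planned sample. Any bias in the mean rests on assumed values of *m* and *d*, and the retention gap rests on a reporting rule that the documents do not contain. This conclusion assumes that staff apply 4.2.2 as written. It would weaken only if the team treated discontinued participants as outside the final assessment, which no passage tells them to do.

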2.1 Primary Objective (or Aim)

The primary objective of this study is to determine whether a 10-session behavioral activation support program is feasible and acceptable to people with cardiovascular risk who have experienced homelessness. The outcomes we will use to assess this treatment development phase of our work will be our ability to recruit and retain participants, the dose of treatment we can deliver (i.e., participant's attendance and follow-up with scheduled sessions and treatment activities), and participants' report of their satisfaction and overall experience during participation in a structured survey and qualitative interview.

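### Section 4.6 lets the investigator remove a participant from the study for poor attendance, although attendance and retention are the primary feasibility outcomes

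*Combined protocol and SAP*

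**What the plan says.** Three sections make staying in the study and attending sessions primary outcomes. Section 1.3 states: "We will also examine treatment engagement and retention via the number of attended assessment visits and coaching sessions". Section 2.1 names "our ability to recruit and retain participants, the dose of treatment we can deliver" as outcomes for the primary objective, and Section 6.1 repeats this for the primary endpoint ("measuring our ability to recruit and retain participants, the dose of treatment we can deliver"). Both explain dose as attendance at, and follow-through with, scheduled sessions and activities.

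Section 4.6 then says that participants may be "discontinued from the study at the discretion of the Investigator for lack of adherence to study treatment or visit schedules", and names adverse events as a further ground. The rule is permissive, sets no threshold, and acts on study participation as a whole.

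Three places deal with assessment after an early stop:

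- Section 3.1.3: "Participants who have completed their planned coaching sessions or requested to end their coaching sessions early will be contacted for a follow-up assessment". It adds that "those ending early will be given particular attention during their post-treatment interview".
- Section 4.6.1 opens with "Any participant who withdraws will be contacted by" and goes on to offer a paid final assessment to those who are willing.
- Section 4.2.2: "The final assessment visit will be completed within 4 weeks of completion of visit 10 or upon early termination".

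Section 6.2.2 plans communication counts by modality and initiator, total treatment minutes and session notes. It does not state a denominator for retention, and does not commit to separating stops by staff from stops by participants.

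**The concern.** Missed sessions and visits are what this trial is designed to observe. Under Section 4.6 they are also a reason for staff to close a participant's record. Once that happens, no further sessions are offered and the later visits may not take place. A low session count or an absent final visit would then partly reflect a discretionary decision by the investigator, and not only how far people in this population engage.

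The people affected are also among the most informative. Section 3.1.3 says that the experience of early enders should shape later versions of the intervention. Their satisfaction score and exit interview are part of the primary acceptability data. At stake is how clearly the attendance and retention figures can be carried into the planned randomized pilot.

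**Working it through.** The plan gives no retention target, no expected discontinuation rate and no calculation behind the sample size of 8 (Section 6.3 gives reasons in words only). There is no figure of the plan's own to reproduce, so the check is a comparison of texts plus one proportion.

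**1. Does the rule act on the primary outcome?** Sections 1.3, 2.1 and 6.1 measure attended visits, attended sessions and retention. Section 4.6 makes poor adherence to treatment or to the visit schedule a ground for leaving the study. Trigger and outcome are the same behaviour. Section 4.6 does not limit the consequence to coaching.

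**2. Is a person stopped by staff still assessed?** The sentence in 3.1.3 on who is contacted covers those who completed and those who asked to stop. Section 4.6.1 covers those who withdraw. Neither names people stopped by staff. Section 4.2.2, however, attaches the final assessment to early termination without saying who terminates. The wording is therefore unclear, but it does not exclude these people.

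**3. Size for retention.** Inputs: N = 8 (Section 3.3.2), and one participant stopped by staff. Assumption: retained means attending the final assessment, since the plan does not define a retention proportion.

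- Change in retention = (participants stopped by staff who have no final visit) / N.
- Final visit still attended: 0/8 = 0 points.
- No final visit: 1/8 = 12.5 points, for example from 8/8 = 100% to 7/8 = 87.5%.

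For scale, exact (Clopper-Pearson) 95% intervals are 63.1% to 100% for 8/8 and 47.3% to 99.7% for 7/8. The shift lies well within the sampling uncertainty of eight people. The problem is therefore what the number means more than its precision.

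**4. Size for attendance.** This cannot be fixed. It depends on when the stop occurs, how many sessions were still planned, and how many of those the person would have attended. The documents give none of these for a non-adherent participant, and Section 1.3 plans 8 to 10 sessions, not a fixed 10. If the person would have attended no more sessions, the loss is zero.

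**The case against.** The strongest reply is that the protocol already leans towards keeping people in. Section 3.3.1 gives four weeks for missed visits and the final assessment. Sections 4.2 and 4.3 provide several contact routes and reminders, and Section 1.4 allows the number and length of sessions to be adapted. The discontinuation rule only permits, and someone stopped under it has already shown the poor adherence that the trial wants to detect. With eight participants, session notes and communication counts would probably make a staff stop visible, and the Assessment Table and case report form, which are not among the documents supplied, may record the reason. All of this stands, and it keeps the point modest. It does not remove it: looking at cases afterwards cannot recover sessions never offered or an interview never held.

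Four stronger readings are tempting, and the documents do not support them.

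- A reader might infer that people stopped by staff are shut out of follow-up. Section 4.2.2 does not limit who terminates. The last sentence of Section 4.6 recognises only completing or withdrawing, and Sections 8.4 and 9.4.1 use withdrawal for removals that professionals recommend. Section 4.6.1 can therefore be read to include them.
- A reader might infer that such a participant would leave the denominator, giving 7/7 in place of 7/8. Nothing in the text suggests this.
- A reader might want a figure for lost sessions or minutes. Any such figure would rest on invented attendance and an invented stopping point.
- A reader might infer that stops for missed visits would distort the early-termination rate used for safety in Section 5.4. The text does not say how such stops would be classified, so this is speculation.

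**Conclusion.** The concern holds for the rule itself. Section 4.6 allows a discretionary exit from the study, without a threshold, on the very behaviour that the primary outcome measures. Using it would end that measurement and blur staff decisions with participant disengagement. At N = 8, one affected participant changes retention by 12.5 points if there is no final visit and by nothing if there is one. This assumes that retention is read from attendance at the final assessment. How often the rule would be invoked is unknown. The study is descriptive, and no test, threshold or stated decision changes, so this is a worthwhile low-cost improvement and not a threat to the trial's validity.

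**What to change.** - **Section 4.6:** let lack of adherence end coaching only, not study participation. Keep adverse events as a ground for discontinuation.
- **Section 4.6.1:** state that participants whose coaching is ended by staff are offered the final assessment, the CSQ-8 and the exit interview on the same terms as those who withdraw.
- **Section 6.2.2:** report retention over all enrolled participants, and list for each one who ended coaching and why. The listing is needed even after the change to 4.6, because a staff decision to end coaching would still shorten that person's session count.

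The cost is a few sentences and a table of at most eight rows. The downside is continued contact attempts with people who are not attending, up to week 16, a period that Section 3.3.1 already sets aside for missed visits and the final assessment. Participants keep their right to decline.
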